Short-Term PCR Attenuates Intimal Hyperplasia Restenosis is a recurrent problem from vascular patients and applicable to a range of procedures. While fortunately an infrequent event, restenosis after CEA can lead to strokes and repeat interventions for patients⁷⁶. In a validated mouse model of the primary driver of restenosis, intimal hyperplasia⁷⁷, we discovered that a short-term pre-operative PCR diet resulted in less intimal area (p=0.032) vs controls. Mice on a PCR diet also had significantly larger internal elastic lamina length (p=0.003), a remodeling measure. Finally, the PCR cohort serum exhibited significant decreases in certain classes of circulating lipids, including a collapse of multiple triglyceride species, suggesting a fundamental shift in metabolism toward beta oxidation. In addition, the lowered levels of circulating triglycerides may help reduce secondary insulin resistance and inflammation.

Approach and Methods

Eighty subjects undergoing carotid artery endarterectomy, aortic aneurysm repair (open, and endovascular if groin cut down planned), open lower extremity arterial procedures (bypasses, aneurysm repair, arterial and bypass graft reconstructions), major amputation of the lower extremity (below knee and above knee amputations), or open hemodialysis procedures either symptomatic or asymptomatic disease will be recruited and enrolled at BWH. Using a randomized (3:2), parallel design, patients will receive either the PCR diet (n=48; ScandiShake [any of 4 flavors] mixed with almond milk, calculated individually for a total daily volume to achieve 30% caloric restriction and 70% protein restriction, based on body weight and activity level), or continued routine *ad libitum* diet (n=32). The Mifflin St. Jeor equation will be used to calculate the total 24-hour energy needs based on gender, age, height, weight, and activity factor for the PCR diet. Daily physical activity will be assessed by questionnaire to determine the activity factor for accurate calorie restriction calculations. The general ratio recipe for the ScandiShake is 85 grams ScandiShake powder to 240 cc almond milk. Water

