intake is ad libitum for both cohorts, and both diets can be consumed throughout the day and night (except on the day of surgery). We have selected the ScandiShake as the PCR diet because it is currently the lowest protein shake available and there are other trials ongoing with this approach, though none [except our prior pilot study] are in vascular surgery patients. We paired the shake with almond milk since it is also low protein. Patients will consume their assigned diets for the four days leading up to surgery until midnight the day of surgery when both cohorts will be NPO.

Inclusion Criteria: Patients greater than 18 years old who present for one of the following elective procedures at BWH:

- Carotid artery endarterectomy
- Aortic/iliac aneurysm repair (open, and endovascular if groin cut down planned)
- Open lower extremity arterial procedures (bypasses, aneurysm repair, arterial and bypass graft reconstructions)
- Major amputation of the lower extremity (below knee and above knee amputations).
- Open hemodialysis access procedures

Exclusion Criteria: Patient intolerance or allergy to any of the ingredients in the PCR diet; Active infection; Pregnancy; Malnutrition, based on abnormally low serum albumin (lower than 3 g/dL); Uncontrolled diabetes (HgbA1c greater than 12%); Substance dependency that could interfere with protocol adherence and assent as determined by the PI; Active non-cutaneous cancer under treatment with chemotherapeutics or radiation; Emergency surgery; Active participation in any another interventional or randomized study; Participation in the current study within the past 30 days.

Recruitment

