Subjects will be recruited through the BWH Vascular Surgery outpatient clinics and inpatients wards. Physician-Investigators will notify the study coordinators about candidates that fit inclusion/exclusion criteria. Study coordinators may discuss the study with potential subjects in detail and answer questions about the research being conducted. Patients will be introduced to the study in outpatient clinics or inpatient units and given ample time (>12 hours) to consider enrollment. Patients will be provided with the opportunity to discuss the trial with family or another physician if they wish to consent at a later time. Consent will only be obtained by a licensed Physician Investigator. All patients screened for this study will either have an established relationship with the physician-investigator or an established collaboration between a clinician known to them and the physician-investigator. Only with the collaborative clinician's approval may the investigator or study coordinators approach the patient about the research trial. Once the patient's permission has been obtained, screening tests and procedures will be performed to determine subject eligibility.

If the patient consents and remains eligible for the study, then the subject will then be randomized. This randomization will occur before the OR event to allow for resources preparation, baseline testing, and dietary intervention.

Foreseeable Risk and Discomforts

Patients randomized to the PCR diet may have a difficult time adhering to the PCR four-day diet, however our pilot data shows that it is feasible for vascular patients to adhere to the diet pre-operatively. We hope to alleviate this by introducing a variety of flavors that patients may choose from. Furthermore, by requiring the patient to log their meals with either the MealLogger app or paper record, we can closely monitor and control dietary intake while also allowing the patient to continue their normal lifestyle before surgery.

Patients randomized to the PCR diet may also experience hunger or discomfort higher than normal from limiting their diet for four days. We hope that with additional flavors some discomfort can be alleviated. If the patient feels too hungry or uncomfortable they may choose to withdraw from the study. Patients may also experience fatigue pre-operatively if randomized to the PCR diet. Based on our pilot data of PCR diet research in humans, patients were able to complete the diet safely and without excess risk.

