The focus of this Mechanistic Trial is to gain insights into practical future trial construction considerations such as patient compliance and physiologic impact. We anticipate that the supervised PCR will be completed by a majority (~80%) randomized to that arm and that H_2S and H_2S production capacity will rise on day two and be significantly elevated above baseline until re-feeding POD#1. We expect that markers of stress will change significantly less in the active treatment group compared to normal diet group. Using an α of 0.05 and β of 0.8, based on the differentials observed in rodent work and factoring in non-compliance, via intent-to-treat the study is powered to test these two primary scientific markers (H_2S and norepinephrine/IL-6). Furthermore, we believe that there will be no significant adverse effects of the H_2S upregulation and PCR diet but do expect a 20% dietary compliance failure rate. Based on our own pilot work, we anticipate that markers of inflammation will be elevated (compared to non-atherosclerotic patient's samples in hand) in the enrolled subjects and further amplified by the surgical stress. We anticipate that the blood and adipose phenotypic signatures will have high inflammation, but that the subjects compliant with PCR will have a reduced global inflammatory activation state, and trends toward less carotid plaque inflammation and fewer postoperative complications. Our key endpoint for upregulation of endogenous hydrogen sulfide will be the P3 cell sorting assay. Based on pilot data we anticipate a 4% increase in the PCR diet cohort compared to ad lib diet controls, with an expected standard deviation of 8%. Using a power of 80% and an alpha of 0.05, and 8% specimen loss rate we need a sample size of $n=80$ to reach statistically meaningful conclusions (un-paired T-test). Importantly for future trials, we anticipate that the unbiased discovery platform will generate novel mechanistic hypotheses founded on human data and tissues that will be ripe for future research and translation.

References

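### Does a re-entry bar of only 30 days undermine a parallel comparison of 80 subjects?

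*Combined protocol and SAP*

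**What the plan says.** Under Approach and Methods, the last exclusion criterion is "Participation in the current study within the past 30 days". It does not say whether the 30 days run from consent, randomization, surgery, the day-30 visit or the end of follow-up. The criterion before it, "Active participation in any another interventional or randomized study", concerns other studies and so does not block a return to this one. Under Recruitment, "If the patient consents and remains eligible for the study, then the subject will then be randomized", with no once-per-patient condition.

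The same Approach and Methods section describes the sample as "Eighty subjects undergoing carotid artery endarterectomy" or one of the other listed procedures, and the design as follows: "Using a randomized (3:2), parallel design, patients will receive either the PCR diet" (48) or the usual diet (32). Statistical Considerations sizes the P3 assay, the key endpoint for hydrogen sulfide, with an unpaired t-test. No section says how a second record from the same person would be analysed.

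On whether repeats can arise, the background on intimal hyperplasia says: "While fortunately an infrequent event, restenosis after CEA can lead to strokes and repeat interventions for patients". Bypass graft reconstructions are also among the eligible operations. The documents give no expected number of returning patients.

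**The concern.** An unpaired t-test treats all 80 records as independent. Two records from one person are correlated, and a person who appears in both arms has no natural place in a parallel comparison. A time-limited bar seems to permit exactly this.

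Three results could be affected: the type I error and power of the P3 test, the precision of the compliance estimate, and the one-year outcomes. If the 30 days run from surgery, a second entry could fall inside the first year of follow-up, and one death or cardiovascular event could then be counted in both arms. Vascular patients do come back for further operations, so the possibility cannot be ruled out.

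**Working it through.** **Inputs from the plan.** 48 and 32 per arm (Approach and Methods); P3 difference 4, SD 8, alpha 0.05, power 80%, specimen loss 8%, expected completion about 80% (Statistical Considerations).

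**Assumptions.** R repeat patients, R = 0 to 5; within-patient correlation ρ between 0.3 and 0.8; no carry-over from the first four-day diet into a later entry. None of these is in the documents.

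**The plan's own figure.** With a two-sided test at 3:2, the control arm needs (1 + 1/1.5) × (1.96 + 0.8416)² × (8/4)² = 52.3, so 53. The PCR arm needs 1.5 × 53, so 80. The total is 133 before loss and 133/0.92, so 145, after it. The stated 80 is not reproduced; at 48:32 with no loss, power is 0.58. That is a separate matter. Here the comparison is between 80 records with and without repeats.

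**1. Where a repeat patient lands.** Under fresh 3:2 allocation: both PCR 0.6² = 0.36; both control 0.4² = 0.16; one of each 2 × 0.6 × 0.4 = 0.48.

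**2. Variance of the P3 difference.** Relative to independent records, with k the number of repeat patients of each type,

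factor = 1 + ρ × [2k(PP)/48² + 2k(CC)/32² − 2k(cross)/(48 × 32)] / (1/48 + 1/32).

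Per repeat patient this adds 0.0167ρ (both PCR), adds 0.0375ρ (both control) or subtracts 0.025ρ (cross-arm). The expected change is 0.36 × 0.0167 + 0.16 × 0.0375 − 0.48 × 0.025 = 0.006 + 0.006 − 0.012 = 0.

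**3. Extremes at ρ = 0.8.** Two-sided alpha = 2 × [1 − Φ(1.96/√factor)].

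| R | All cross-arm: factor, alpha | All control-control: factor, alpha | Chance all are control-control |
|---|---|---|---|
| 1 | 0.98, 0.048 | 1.03, 0.054 | 16% |
| 2 | 0.96, 0.046 | 1.06, 0.057 | 2.6% |
| 3 | 0.94, 0.043 | 1.09, 0.060 | 0.4% |

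**4. Simulation.** 80 records were allocated 48:32 and analysed by the unpaired t-test. With 4, 8 or 16 patients entered twice and ρ of 0.3, 0.5 or 0.8, the type I error was 0.048 to 0.052 (0.050 with no repeats) and power 0.579 to 0.585 (0.580 with none). A further simulation with 0 to 16 repeats at ρ = 0.8 gave a mean difference of about 4.01 for a true 4, alpha 0.048 to 0.053 and power 0.581 to 0.584.

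**5. Compliance.** The plan specifies no interval. A 95% half-width at 80% of 48 is 1.96 × √(0.8 × 0.2/48) = 11.3 points. Averaged over allocation at ρ = 0.8, multiply by √(1 + 0.36 × (2/48) × 0.8R) = √(1 + 0.012R). If every repeat is PCR-PCR, multiply by √(1 + 2 × 0.8R/48).

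| R | Average | Maximum |
|---|---|---|
| 1 | 11.4 | 11.5 |
| 2 | 11.5 | 11.7 |
| 3 | 11.5 | 11.9 |
| 5 | 11.7 | 12.2 |

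**6. One-year events counted in both arms.** The expected number is R × 0.48 × p. With an assumed event risk p of 5% to 20% after the second entry and overlapping follow-up, this is 0.02 to 0.10 for R = 1 and 0.12 to 0.48 for R = 5. If participation ends at one year, where the schedule in Data Collection appears to place it, re-entry is barred until about 13 months and the figure is 0.

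**The case for a change.** The best case for a change concerns clarity rather than bias. The text is silent on what happens when a patient returns, so staff and analyst would have to decide when it happens, perhaps with data in view. Restricting each person to one randomization would take one line, would leave the target at 80, and would cost few candidates when about 600 are to be screened. Even if the 30-day rule is meant to allow later re-enrolment, the plan still lacks a start date and a rule for the second record.

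The description of the text stands: the gap is real. What does not stand is that filling it improves a result. The P3 comparison is unbiased with or without repeats, and its average operating characteristics do not move. A total ban is also only one reasonable remedy. Using the first record only, or a model that allows for within-patient correlation, would serve as well, and choosing among them is preference. The likelihood of repeats is also thinly supported. The protocol calls restenosis after carotid surgery infrequent, and a second entry needs another eligible elective operation, renewed eligibility and renewed consent.

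**Conclusion.** No change is needed. The wording is loose, but the natural reading of a parallel trial in 80 subjects is 80 people with one arm each, and nothing in the documents shows an intention to count anyone twice. If a patient did return, an analyst would see the repeated person and could keep the first randomization or allow for the pairing.

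If nobody did so, the expected change in the variance of the P3 difference is zero. An alpha as high as 0.060 needs three repeats, all control-control, at a correlation of 0.8, which has a 0.4% chance. The compliance half-width widens by less than one point even at the maximum for five repeats. The double-counting concern is confined to one-year outcomes that the plan calls exploratory, amounts to less than half an expected event at five repeats, and disappears if participation runs to one year.

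These sizes rest on an assumed number of repeats and correlation and on no carry-over between entries. With no repeats there is no effect at all. Stating when the 30 days begin, and that the first randomization is the one analysed, would be an optional tidying that changes no expected result.

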Chronic protein and calorie dietary restriction (PCR; reduced food intake without malnutrition) is known for extending longevity in multiple species¹⁸. PCR is also an established approach to positively impact metabolic fitness and resistance to multiple forms of acute stress¹⁹⁻²¹. Despite these wide-ranging benefits, potential clinical applications have never been considered feasible in humans due to the practical difficulties associated with voluntary food restriction combined with the assumption that PCR benefits take a long time to accrue. Recent preclinical studies by the applicants reveal a rapid onset of PCR benefits against surgically induced traumatic inflammation, IR injury, and the fibroproliferative vascular response to injury in rodents^{14-17, 22, 23}. Mechanistically, rapid changes in adipose phenotype and associated adipokine profiles appear to underlie these benefits¹⁶; but the key mediator appears to be endogenous H₂S. This field thus stands poised to move to clinical utility, and vascular surgery offers an optimal risk/benefit ratio for translation of the PCR/H₂S hypothesis¹⁵.

For the current project we propose a randomized, controlled trial to evaluate patient compliance and biologic mechanisms of a short-term pre-operative PCR diet in comparison to a normal ad libitum diet for 4 days before elective vascular surgery involving an open major operation. Both Endpoints relate to the long-term primary scientific objective to test the hypothesis that ***brief upregulation of endogenous H₂S via pre-operative PCR in elective major surgery improves clinical outcomes in humans***. After a successful pilot study of the PCR diet conducted inpatient before carotid endarterectomy titled Short-Term Endogenous Hydrogen Sulfide Upregulation (PHRC Protocol No. 2016P002507), we now aim to expand the study to at home diet among a variety of vascular surgery procedures. The primary endpoints of the study are:

- 1) Feasibility, and in particular outpatient subject compliance with PCR (measured by direct dietary intake data and serum markers including plasma free amino acids, pre-albumin, and insulin-like growth factor in comparison to the ad libitum diet).

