Data Collection

Time	< 30 Days Pre-op (Baseline)	4 days Pre-Op	3 days Pre-Op	2 days Pre-Op	1 day Pre-Op	Day of Op (Pre-Op)	Recovery Area	Post- Op Day #1	Post- Op Day #30 (+/- 14 days)	Post- Op 1 Year
Patient Screening (estimated n=600)	Enrollment, Randomization, Education (n=80)	Control Continue Usual Dietary Pattern (2:5 randomization)						NPO except meds	Resume Usual Diet	Study Participation Terminates
		Dietary Restriction Protein-Calorie Restriction x 4 days (3:5 randomization)						NPO except meds		
MealLogger app Entry		X	X	X	X	X	X		→ Post Op Day 14	
Blood Draw						X	X			
CBC with diff, Chem 7, lipidomics, cortisol, epinephrine, norepinephrine, dopamine, hs CRP, IL-6, leptin, HMW adiponectin, resistin, IGF-1, P3, serum pregnancy test (as needed); pre-albumin (baseline and preop)		X								
Determinations										
Physical Activity Questionnaire	X									
24-Hour Food Recall	X									
Height, Weight	X					X	X		X	
eGFR	X					X	X			
Wound Evaluation								X		
Tissue Collection*						X				
Full Medical History	X								X	
Satisfaction Questionnaire									X	
Physical Exam	X								X	
Chart Review										X
	Preprocedure					Inpatient		Post Procedure		Registry

*discarded artery, vein, peri-vascular or subcutaneous fat, aneurysmal specimens, and amputated tissues

Dietary compliance will be measured by way of dietitian calculated intake (for data analysis will be the gold standard). The subjects will be asked to document their meals using either the MealLogger app or paper

record. The MealLogger app allows subjects to take a picture of their meals, either the ScandiShake or their routine ad libitum diet. Study dieticians will interpret dietary intake through photos and directly contact subjects using the app for clarification of intake, or through paper record if subjects are unable to use the MealLogger app. Compliance with the dietary intervention will also be evaluated through measuring expected changes in the levels of plasma amino acids using an LC-MSMS platform, and insulin-like growth factor-1 (IGF-1) by ELISA. Because free amino acids are not stored in the body, PCR results in a rapid decline of essential amino acids, including methionine and tryptophan, that are monitored easily in blood plasma^{79, 80}. Isolated protein restriction also results in reduced plasma IGF-1, even in the absence of overall PCR⁸¹.

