H_2S and H_2S production capacity (two distinct entities, see *Cell* paper¹¹) will be longitudinally measured, as will stress and safety markers in blood samples taken prior to dietary intervention (PCR or control), after the dietary intervention but before surgery, and sequentially after vascular surgery. Blood samples will also be collected and analyzed by [name] team at Northwestern to assess for changes related to PCR. Adipose tissue biopsies from fat depots (subcutaneous, perivascular) will be taken at the time of surgery and analyzed for the effects of diet on lipid composition and on inflammatory markers predictive of the response to surgical stress. Additionally, discarded specimens (discarded artery, vein, peri-vascular or subcutaneous fat, aneurysmal specimens, and amputated tissues) will be collected and stored for microscopic analysis. Enrolled patients and their clinical data will be entered into a study-specific database within REDCap.

Statistical Considerations

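### PCR patients who cannot tolerate the diet are offered exit from the study, not from the diet alone, so post-diet blood samples may be lost selectively from the PCR arm

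*Combined protocol and SAP*

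**What the plan says.** - **Foreseeable Risk and Discomforts.** The PCR arm is warned of hunger: "Patients randomized to the PCR diet may also experience hunger or discomfort higher than normal from limiting their diet for four days". More flavours are offered to ease this. The next step given is: "If the patient feels too hungry or uncomfortable they may choose to withdraw from the study". Difficulty adhering is treated in a separate paragraph and answered with flavours and meal logging.
- **Project Goals/Specific Aims.** The first primary endpoint is "Feasibility, and in particular outpatient subject compliance with PCR (measured by direct dietary intake data and serum markers", set against the ad libitum arm. The second is H₂S and stress markers in blood.
- **Approach and Methods.** Allocation is 48 PCR to 32 control. On duration: "Patients will consume their assigned diets for the four days leading up to surgery until midnight the day of surgery".
- **Data Collection.** Blood is taken before the diet and then "after the dietary intervention but before surgery, and sequentially after vascular surgery". On adherence: "Dietary compliance will be measured by way of dietitian calculated intake (for data analysis will be the gold standard".
- **Statistical Considerations.** About 80% of those randomised to PCR are expected to complete it, and the investigators "do expect a 20% dietary compliance failure rate". The analysis claim is "factoring in non-compliance, via intent-to-treat the study is powered to test these two primary scientific markers", the markers being H₂S and norepinephrine/IL-6. P3 is the key H₂S assay, planned on a difference of 4 points, SD 8, and 8% specimen loss.

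The protocol gives no step for stopping the diet while remaining in follow-up. It has no rule for counting withdrawn patients in endpoint 1 and no method for their missing blood results.

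**The concern.** Intent-to-treat needs outcome data from patients who did not follow their assigned diet. Here the only exit described for a patient who finds the diet intolerable is from the whole study, and it falls before any post-diet blood. Controls eat as usual and have no matching reason to leave.

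The loss would be informative. Those who leave for hunger are likely to be diet failures, and adherence is what the first primary endpoint measures. Without them, the PCR arm's amino acids, IGF-1, pre-albumin, P3 and stress markers come from a more adherent subset. Separation between arms could then look larger than in all randomised patients. The trial is meant to inform later trials on compliance and physiological effect, so that picture would carry forward into their planning.

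**Working it through.** **Timing.** The diet continues to the night before surgery. Apart from baseline, blood is taken after the diet but before surgery, and again after surgery. A withdrawal for hunger during the four days therefore precedes every post-diet sample.

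**The plan's own figures.** Expected failures are 0.20 × 48 = 9.6, taken as 10, leaving 38 compliers. 38/48 = 79%, which agrees with the stated completion of about 80% of those randomised. The specimen allowance is 0.08 × 80 = 6.4.

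The stated total of 80 does not reproduce. With a two-sided test and 3:2 allocation, controls = (1 + 1/1.5) × (8/4)² × (1.960 + 0.842)² = 52.3, rounded up to 53. PCR is 80, the total is 133, and 133/0.92 gives 145. Other standard variants give 109 to 137. That is a separate matter; the present point does not depend on it.

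**Range.** The documents give no withdrawal rate, so k = 0, 5 or 10 of the 10 failures are assumed to withdraw, leaving n = 48 − k. Laboratory loss of 8% is applied to those left. The plan gives 4 points for the PCR cohort; treating it as the effect in compliers is an assumption.

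| Quantity | k = 0 | k = 5 | k = 10 |
|---|---|---|---|
| PCR patients remaining (n) | 48 | 43 | 38 |
| PCR patients with samples, 0.92n | 44.2 | 39.6 | 35.0 |
| PCR sample loss, 1 − 0.92n/48 | 8% | 18% | 27% |
| Control sample loss | 8% | 8% | 8% |
| P3 difference, failures at 0: 4 × 38/n | 3.17 | 3.53 | 4.00 |
| P3 difference, failures at 2: [4 × 38 + 2 × (10 − k)]/n | 3.58 | 3.77 | 4.00 |
| Compliers among those remaining, 38/n | 79% | 88% | 100% |
| Compliers among all randomised, 38/48 | 79% | 79% | 79% |

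At the extreme, 4.00/3.17 = 1.26. Seven withdrawals would exceed the 6.4-specimen allowance, all in one arm.

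**Power, two-sided t-test, SD 8.** With everyone retained and failures at 0, a difference of 3.17 with 44.2 against 29.4 samples gives 0.375. With all 10 gone, 4.00 with 35.0 against 29.4 gives 0.503. The second figure is higher only because the diluting patients are absent. With the difference held at 4 and no laboratory loss, losing 10 PCR patients moves power from 0.58 (48 against 32) to 0.54 (38 against 32).

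**The case against.** The sentence states a voluntary right in a risk section. It is not a disposition or analysis rule. Much of the case built on this stands, and it rules out several stronger readings.

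- **A reader might infer that non-compliers will be lost.** The text says only that a patient may choose to leave, for hunger or discomfort. Some who fail the diet will stay, and nothing in the plan removes them. Nor does the plan say that controls cannot withdraw; only this particular reason is confined to the PCR arm.
- **A reader might infer that endpoint 1 will read 88% or 100%.** That needs a denominator of patients remaining, which the plan never states. Its completion expectation is based on those randomised. A withdrawal is observable and can be counted as a failure. Intake logged before exit already exists, and nothing says it is discarded.
- **A reader might set 20% failure against 8% specimen loss as a contradiction.** They are different quantities and compete only to the extent that failures become withdrawals.
- **A reader might take 26% as the expected bias.** It requires every failure to withdraw and to have no P3 response. With half withdrawing and a half response, the figures are 3.58 and 3.77, a small gap against an SD of 8. The inpatient pilot also reported that patients could complete the diet.

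The consent pages are not in the text reviewed and might say more about stopping the diet.

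One part of the concern survives all of this. Counting withdrawals as failures rescues the completion proportion but does not supply their serum markers, P3, norepinephrine or IL-6.

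**Conclusion.** The concern holds in limited form. The protocol directs diet intolerance towards study exit, before every post-diet sample, and offers no route for stopping the diet and staying in. Blood data may therefore be lost selectively from the PCR arm, which weakens the intent-to-treat comparison of P3, norepinephrine/IL-6 and the serum compliance markers. Completion status is not lost.

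The size is unknown. On the plan's 20% failure rate it lies between 0 and about 10 of 48 PCR patients, and there is no bias if no one withdraws. The P3 overstatement runs from nothing to 0.83 points (4.00 − 3.17). The upper end rests on two assumptions: all failures leave and none would have responded. This should be corrected because the remedy is cheap and the loss cannot be repaired afterwards. It does not show that the trial's results will be biased.

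**What to change.** 1. **Foreseeable Risk and Discomforts.** Replace the withdrawal sentence. A patient who cannot tolerate the diet may stop it, return to usual food and remain in the study for the scheduled pre-operative and post-operative samples and 30-day follow-up. Only withdrawal of consent ends data collection.
2. **Data Collection.** Record the date and reason for stopping the diet.
3. **Statistical Considerations.** Report compliance over all patients randomised to PCR, counting those who stop or withdraw as non-compliant. Report missing samples by arm and reason.
4. **Optional P3 sensitivity analysis.** Where a sample is missing, impute from the control arm, preferably by multiple imputation, only for PCR patients who withdrew or stopped the diet. Laboratory losses should be left out of this. Giving the control mean to them as well would shrink 3.17 to 3.17 × 0.92 = 2.91 even if no one withdrew. Single mean imputation also understates variance.

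The cost is one changed sentence, two database fields and some reporting. No visits are added, because the samples are taken around an operation the patient attends anyway. The downside is that retained non-compliers dilute the P3 difference (3.17 rather than 4.00 in the extreme example), so power for the same n is lower, about 38% against 50% under those assumptions. The lower figure is the one that belongs to the intent-to-treat effect. Some patients will still decline further samples.
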